## 1. Introduction

### 1.1 Overview of the Problem

HIV infection among men who have sex with men (MSM) in Vietnam continues to rise, with prevalence in Ho Chi Minh City (HCMC) estimated at 17% and incidence among young MSM (YMSM) in Hanoi at 5.8%. Behavioral risks such as unprotected sex, multiple partners, and untreated STIs sustain high levels of circulating virus within MSM networks. Low HIV testing rates and poor engagement in care further exacerbate transmission. Meanwhile, widespread smartphone and internet use among Vietnamese MSM offers an opportunity for online testing innovations.

### 1.2 Supporting Evidence

National surveillance shows that HIV prevalence among MSM increased from 6.2% in 2006 to 14% in 2009 in HCMC, reaching 19% nationwide by 2011. Epidemiological studies identify consistent risk factors including low HIV knowledge, sexual risk and STIs, identity- and stigma-related challenges, and limited access to appropriate health services. A Vietnam-based survey found that 76.5% of MSM had never been voluntarily tested for HIV. Evidence from Thailand demonstrates that an online HIV testing (OHT) model achieved 90% retention and 100% linkage to care. Additionally, 97% of Vietnamese MSM report HIV self-testing as acceptable.

### 1.3 Rationale for This Study

Persistent barriers such as stigma, low perceived risk, and fear of disclosing same-sex behaviour continue to limit HIV testing among Vietnamese YMSM. Increasing HIV testing is essential for achieving the UNAIDS 90-90-90 goals, which require individuals at high risk to test at least annually. Online HIV self-testing with real-time supervision can overcome institutional and psychological barriers while ensuring linkage to treatment or prevention. Building on successful online HIV self-testing with online supervision (STOS) implementation in Thailand, adapting this model for Vietnam could substantially increase testing uptake and reduce HIV incidence.

### 1.4 Objective

Aim 1: To conduct focus group discussions to identify potential barriers and facilitators to the uptake of online HIV testing among YMSM in Ho Chi Minh City

Aim 2: To adapt the existing Thai online HIV self-testing with online supervision intervention for use among YMSM in Vietnam, willingness to engage in online HIV self-testing with online supervision as well as factors related to sustained testing will be collected through an online survey

Aim 3: To demonstrate the feasibility and acceptability of the adapted online HIV self-testing with online supervision (STOS) intervention, including use of an HIV rapid diagnostic antibody/antigen-based self-testing with an HIV counselor through video conferencing

## 2. Study design and methods of data collection

This study aims to evaluate the effectiveness of the HIV self-testing with online supervision (STOS) intervention, which includes the introduction of a HIV rapid diagnostic antibody/antigen-based self-testing conducted with the support of a trained counsellor via video conferencing, among young men who have sex with men (YMSM) aged 16–29 years.

The study employs a pilot randomized controlled trial (RCT) design with two groups: an intervention group (STOS) and a control group. The total sample size is 100 participants (50 per group). The follow-up period spans 12 months, with data collected at three time points: baseline, 6 months, and 12 months.

Data collection includes self-administered online questionnaires completed through the Qualtrics platform. For participants in the intervention group, the study involves the implementation of real-time online supervised HIV self-testing conducted by a trained counsellor through video conferencing.

## 2.1 Procedures

### 2.1.1 Recruitment and Enrollment

Participant recruitment will be conducted over a one-year period, using a combination of online and offline outreach strategies to reach the target population of young men who have sex with men (YMSM) in Ho Chi Minh City.

For the online cross-sectional survey, recruitment will primarily be conducted through online platforms, including Google advertisements, Facebook, the CARMAH fan page, CARMAH networks, other MSM community networks, and youth networks in Ho Chi Minh City (such as university and high school students). To encourage participation, each respondent will receive a mobile top-up e-voucher valued at 50,000 VND (approximately 2 USD), delivered via SMS.

Individuals interested in participating will complete an online eligibility screening form. Those who meet the inclusion criteria will receive detailed study information and proceed with the initial electronic consent (e-consent). After completing the survey, if an individual is found to be HIV-positive, they will not be invited to participate in the pilot study.

For the pilot study, a total of 100 Vietnamese YMSM will be recruited and followed for 12 months. Participants will be randomly assigned into two groups of 50 each:

- The intervention group, which will receive the HIV self-testing with online supervision (STOS) intervention; and
- The control group, which will refer to the standard of care, consisting of a voucher for venue-based HIV testing.

The STOS program begins when a counsellor contacts eligible participants via the Zalo communication platform. After confirming eligibility, the counsellor obtains verbal informed consent and schedules an appointment for the HIV self-testing with online supervision (STOS) session.

Once the appointment is confirmed, HIV self-testing kits are delivered to participants through Be Delivery service. Before the testing session, participants receive a link to an instructional YouTube video developed by CARMAH and Mahidol University, which demonstrates the correct procedure for performing the HIV self-test.

During the scheduled session, the counsellor provides pre-test counselling and real-time supervision via video conferencing as participants perform the self-test. This process ensures proper use of the test kit, supports accurate interpretation of results, and maintains participant confidentiality throughout the HIV self-testing process.

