### 2.1.2 Data Collection

Data collection will occur at three time points: at baseline and again at 6 and 12 months of follow-up. During each assessment, participants will complete self-administered questionnaires on tablets or smartphones via the Qualtrics platform. For individuals assigned to the STOS group, HIV self-testing outcomes will be documented by a trained counselor and stored in an encrypted file with restricted access. Only the Principal Investigator (PI) and the Study Statistician will be authorized to view these data to maintain strict confidentiality.

All study data will be housed on secure institutional servers in encrypted, password-protected formats to ensure robust data security.

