## 2.3 Consent

### 2.3.1 Consent Procedures

All participants will provide informed consent by clicking "accept button" at the time they begin the online survey. For participants under 18 years of age, a waiver of parental consent will be obtained from the ethics committee to protect them from the potential risk of unintentional

disclosure of their sexual orientation or HIV status. Before joining the study, participants will receive a study information sheet explaining the research objectives and procedures. This document will appear immediately before the consent question in the online survey, allowing participants to review the study details before providing consent. After completing the survey, participants who are interested in joining the STOS intervention will be introduced to additional information, as follows: Participants will be informed that the study involves an online HIV self-testing intervention and that they may be randomly assigned to one of two testing approaches.

The first approach involves receiving an HIV home self-testing kit, with real-time guidance and support from trained staff via video calls and instructional videos. The second approach involves receiving information about free HIV testing services available at public hospitals, where participants can go for testing independently. If selected for participation, study staff will contact participants using the contact information provided to explain further details and confirm their willingness to take part. For those who are randomly assigned to the STOS group, multiple formats will be used to ensure a full understanding of study procedures. These include printed materials, instructional videos (e.g., how to perform HIV self-testing), and verbal explanations provided by trained counsellor. Participants will be encouraged to ask questions about any aspect of the study, including the survey process, HIV self-testing procedures, and their right to withdraw from the study at any time without penalty or loss of benefits. Informed consent will be obtained only after participants demonstrate clear understanding and express their willingness to participate voluntarily. At each follow-up round, field staff will reassess participants' understanding and verbally reconfirm consent before administering questionnaires or conducting STOS sessions, to ensure that participants remain fully informed and voluntarily engaged throughout the longitudinal study

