## 2. Study Design Overview

This study is a pilot randomized controlled trial (pilot RCT) using a longitudinal cohort design among young men who have sex with men (YMSM) aged 15–29 years, with a total of 100 participants equally allocated into two groups:

- STOS intervention group (n = 50)
- Control group (n = 50)

Participants will be followed for a period of 12 months, with data collection conducted at three times: baseline, 6 months, and 12 months of follow-up.

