#### 3.3 Primary Outcome

- **HIV testing uptake:**

Proportion of participants who report having tested for HIV at least once within a 6-month period, based on STOS testing records and self-reported survey data.

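### The primary model for HIV testing uptake omits testing in the 6 months before baseline, which costs precision but causes no bias

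*Combined protocol and SAP*

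**What the plan says.** Protocol 2 fixes the size: "The total sample size is 100 participants (50 per group"). Protocol 2.1.1 gives the allocation as "Participants will be randomly assigned into two groups of 50 each", and SAP 2 as "with a total of 100 participants equally allocated into two groups". Neither document names a sequence method, blocking or a stratification factor.

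SAP 3.3 defines the primary outcome as "Proportion of participants who report having tested for HIV at least once within a 6-month period". Protocol 2.1.2 sets the schedule: "Data collection will occur at three time points: at baseline and again at 6 and 12 months of follow-up". The model in protocol 2.4.2 and SAP 6.2 is a GEE with arm, time and their interaction. Neither section names a baseline covariate or says whether the baseline round is one of the outcome rounds. Protocol 2.4.1 summarises baseline characteristics by arm, descriptively.

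The survey comes before the randomised study. Protocol 2.3.1 says "After completing the survey, participants who are interested in joining the STOS intervention will be introduced to additional information". Under Aim 2 (protocol 1.4), "factors related to sustained testing will be collected through an online survey". A question on testing in the past 6 months is therefore implied, but not listed.

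**The concern.** Eligibility (protocol 2.2) sets no limit on testing history, and protocol 2.1.1 recruits through open advertising as well as MSM community networks. The sample can therefore mix regular testers with men who seldom or never test. Whether a man tested in the 6 months before entry is the same variable as the primary outcome, measured one period earlier, so it is a natural candidate to predict that outcome. If it does, leaving it out of the model keeps explainable variation in the error term and widens the confidence interval. That matters with 50 men per arm, where the standard error of an uptake difference is about 9 to 10 points.

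The open question about the baseline round adds to this. If it is left out, prior testing is not used at all. If it is included as an outcome, the arm × time term becomes a difference in changes, which can be noisier than a plain follow-up comparison.

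**Working it through.** The documents give no effect size, power or alpha for the 100 men, so there is no stated figure to reproduce.

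**Inputs.** From the documents: 50 per arm, a binary outcome, and one testing-history figure, in protocol 1.2: "76.5% of MSM had never been voluntarily tested for HIV". That implies at most about 24% ever tested in that survey's population. Assumed: 10% to 50% recent testers, a 30- to 40-point difference in later testing between recent and non-recent testers, two-sided 5%, full retention, one follow-up round.

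**1. How large is the chance gap?** With K recent testers among 100 and a fixed 50/50 split, the number X in one arm is hypergeometric(100, K, 50). The arm gap is |2X − K|/50, and the SD of the signed gap is √(4p(1−p)/99), with p = K/100.

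| Recent testers | SD of gap | ≥ 12 points | ≥ 16 points | ≥ 20 points |
|---|---|---|---|---|
| 10 of 100 | 6.0 | 9% | 2% | 0.1% |
| 24 of 100 | 8.6 | 24% | 10% | 3% |
| 50 of 100 | 10.1 | 32% | 16% | 7% |

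The raw uptake difference shifts by the gap times the tester/non-tester difference. A 12-point gap gives 12 × 0.40 = 4.8 points, and a 20-point gap gives 8 points. Both are below one standard error.

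**2. What does omitting the variable cost?** Let Δ be the true uptake difference. Approximate power is Φ(Δ/SE − 1.96), with SE² = (V_STOS + V_control)/50. The per-man variance V in each arm is:
- unadjusted: m(1−m), where m is the arm's overall uptake;
- adjusted: the average of r(1−r) within recent and non-recent testers;
- change from baseline: the adjusted V plus p(1−p)(1−d)², where d is that arm's tester/non-tester difference in follow-up uptake.

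*Half recent; uptake in recent/non-recent testers 92%/65% (STOS) against 75%/35% (control).* m = 0.785 and 0.55, so Δ = 0.235.
- Unadjusted: 0.1688 + 0.2475 = 0.4163; SE 0.0912; power Φ(0.62) = 73%.
- Adjusted: 0.1506 + 0.2075 = 0.3581; SE 0.0846; power Φ(0.82) = 79%.
- Change: d = 0.27 and 0.40; 0.2838 + 0.2975 = 0.5813; SE 0.1078; power Φ(0.22) = 59%.

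*24% recent; 90%/50% against 65%/25%.* m = 0.596 and 0.346, so Δ = 0.25.
- Unadjusted: 0.2408 + 0.2263 = 0.4671; SE 0.0967; power 73%.
- Adjusted: 0.2116 + 0.1971 = 0.4087; SE 0.0904; power 79%.
- Change: 0.2773 + 0.2628 = 0.5400; SE 0.1039; power 67%.

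*Weaker link: half recent; 85%/65% against 70%/40%.* Δ = 0.20.
- Unadjusted: 0.1875 + 0.2475 = 0.4350; power 57%.
- Adjusted: 0.1775 + 0.2250 = 0.4025; power 61%.

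Simulation with robust standard errors (40,000 trials per case) agrees to within about 2 points: 71–73%, 77–78% and 58% in the first case; 74%, 77–78% and 66–67% in the second; 56–57% and 59–60% in the third.

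In the first two cases adjustment cuts the variance by 14% (0.3581/0.4163 = 0.86) and 12% (0.4087/0.4671 = 0.88).

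**3. What would stratified allocation add?** In the first case simulated power with the covariate in the model is about 78% with or without stratified allocation, a difference under 1 point. If allocation is stratified but the analysis is unadjusted, the type I error falls to about 3.5%. With unstratified allocation it stays near 5% (4.7% to 5.4%) whether or not the analysis adjusts.

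**The case against.** A reader might infer something stronger: that a baseline gap large enough to distort the uptake comparison is likely, so allocation must be stratified. The documents do not support this. A 12-point gap has a probability of at most about one in three, and only if half the men tested recently. At the 24% suggested by the one figure in the documents it is about one in four. Chance imbalance under randomisation is already reflected in the confidence interval. It does not bias the estimate or raise the type I error. Unstratified allocation is a legitimate choice in a pilot whose Aim 3 is feasibility and acceptability.

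It can also be said that the arm × time GEE deals with baseline differences. If the baseline round is an outcome round, a gap is indeed differenced out. The text does not say that it is, and differencing is costly here. A change contrast beats a follow-up-only comparison only when the baseline–follow-up correlation exceeds about one half. In the first case the control-arm correlation is 0.40 × √(0.25/0.2475) = 0.40. A stronger link would narrow the deficit.

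SAP 7 allows alternative model specifications, which could include this covariate. That is optional and applies to sensitivity analyses, not to the primary result.

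Two reservations stand. The strength of the link between prior and later testing is assumed, and the survey item is implied rather than listed.

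**Conclusion.** The point holds as a modest, cheap improvement in precision, not as a validity problem. The primary GEE does not use the baseline value of its own outcome as a covariate. Under the stated assumptions, adding it raises power by about 3 to 6 points over an unadjusted follow-up comparison. Against a change-from-baseline contrast the gain is about 11 points (24% recent testers) to 20 points (50% recent).

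These sizes rest on the assumed prevalence of recent testing, the 30- to 40-point link, two-sided 5%, full retention and one follow-up round. For the change contrast they also assume that follow-up testing has no further dependence on baseline given recent testing. Protocol 2.1.3 expects retention above 80%, so actual power could be lower for all three analyses. The calculations use risk differences in place of the GEE, for which protocol 2.4.2 names a log link (rate outcomes) and SAP 6.2 a logit link (binary outcomes).

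The absence of stratification is not itself a defect. Stratifying would balance the raw proportions by arm, which helps when a pilot's figures are passed on, but it adds almost no power beyond the covariate.

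**What to change.** In protocol 2.4.2 and SAP 6.2, write: *HIV testing uptake at 6 and 12 months will be analysed by GEE with arm, follow-up round, arm × round and self-reported HIV testing in the 6 months before baseline (yes/no). The baseline round enters as this covariate and not as an outcome.* Confirm that the pre-randomisation survey or baseline questionnaire contains the item. With a logit link, also report model-standardised uptake proportions by arm, because the adjusted odds ratio is conditional on the covariate.

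The cost is one model term and, at most, one survey question, with no extra visits. The change can be prespecified at any time before outcomes by arm are examined, provided the item was collected.

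Optional, and only possible before enrolment: state the 1:1 blocked allocation method and stratify it on the same yes/no factor. Arm sizes may then differ from 50 by a few men if a final block is incomplete. If allocation is stratified, the stratum must be in the model, because the unadjusted test is then conservative.

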### 4. Analysis Populations

#### 4.1 Intention-to-Treat (ITT) Population

The ITT population will consist of all individuals who completed the baseline assessment and were allocated to either the intervention or control condition, independent of their subsequent engagement with any intervention components. This group will be used as the primary sample for assessing intervention effectiveness, aligning with a real-world evaluation approach that accounts for variations in actual participation.

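### As written, a second eligibility check and verbal consent follow random assignment in the STOS arm only, and no rule covers men who stop there

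*Combined protocol and SAP*

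**What the plan says.** Protocol 2.1.1 opens with steps common to everyone, online screening and electronic consent: "Those who meet the inclusion criteria will receive detailed study information and proceed with the initial electronic consent (e-consent)". For the pilot it then states: "Participants will be randomly assigned into two groups of 50 each". After describing the two arms it turns to the intervention: "The STOS program begins when a counsellor contacts eligible participants via the Zalo communication platform". Within that contact, "After confirming eligibility, the counsellor obtains verbal informed consent and schedules an appointment". The appointment is for the supervised self-test, and the kit is sent only once it is confirmed. The section describes no counsellor check or verbal consent for controls.

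Protocol 2.3.1 tells all interested men, in advance, that they may be randomised to either approach. It has staff contact those selected to give details and check that they still want to join. Neither step is limited to one arm. The section continues: "For those who are randomly assigned to the STOS group, multiple formats will be used to ensure a full understanding of study procedures". Shortly afterwards it says: "Informed consent will be obtained only after participants demonstrate clear understanding and express their willingness to participate voluntarily". Consent is also reconfirmed in both arms before each follow-up questionnaire.

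On the analysis side, SAP 4.1 defines the intention-to-treat population as "all individuals who completed the baseline assessment and were allocated to either the intervention or control condition", whatever their later engagement. Protocol 2.4.2 instead describes the compared STOS group as men who receive a kit and fill in the questionnaires. SAP 5.1 plans multiple imputation or maximum likelihood under missing at random when missingness is substantial, with pattern-mixture sensitivity analyses. It allows complete-case analysis when little is missing and sets no threshold.

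**The concern.** Staff who follow Protocol 2.1.1 in the order it is written would apply an eligibility and consent gate after allocation, in one arm only. A man who balks at a video-supervised HIV test could leave the trial at that gate if he is in STOS. A similar man in the control arm meets no equivalent gate.

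Reluctance to take a supervised test is plausibly related to the primary outcome, which is testing at least once in a 6-month period (SAP 3.3). If such men drop out of the STOS data or are replaced by willing men, STOS uptake rises with no intervention effect. Intention-to-treat membership protects the denominator but does not supply a missing outcome. Imputation under missing at random would not fully correct the loss if refusal carries information about testing beyond the measured covariates.

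**Working it through.** **Order of steps.** The documents give no calculation to reproduce here, so the relevant text is set side by side.

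| Step | Where | Arms | Timing relative to allocation |
|---|---|---|---|
| Online screening and e-consent | Protocol 2.1.1 | Both | Before, by text order |
| Information that assignment is random | Protocol 2.3.1 | Both | Before |
| Staff contact to check willingness | Protocol 2.3.1 | Both | Not stated |
| Counsellor confirms eligibility and takes verbal consent | Protocol 2.1.1 | STOS only | After, by text order |
| Fuller explanation in several formats | Protocol 2.3.1 | STOS only | After |
| Consent once understanding is shown | Protocol 2.3.1 | No arm named | Follows the STOS-only explanation |
| Consent reconfirmed at follow-up | Protocol 2.3.1 | Both | After |

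The asymmetry lies in the counsellor's step and the explanation that goes with it, not in consent as a whole.

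**What happens to a man who stops at the counsellor's step.** Under SAP 4.1 he stays in the analysis set if he completed baseline. Under Protocol 2.4.2, read literally, he is outside the STOS group because he never receives a kit. No section says whether he is surveyed at 6 and 12 months or replaced to keep the arm at 50.

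**Illustration of size.** The documents give no refusal rate and no expected uptake, so all of these inputs are assumptions:
- true uptake p = 0.40 in both arms, with no intervention effect;
- a fraction d of the STOS arm lost at this step, 0.10 to 0.20 (5 to 10 of 50 men);
- uptake u among those lost, 0.10 to 0.20;
- no selective loss of controls.

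Observed STOS uptake among those remaining = (p − d·u) / (1 − d).

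| d | u | Calculation | Observed | Spurious gain |
|---|---|---|---|---|
| 0.10 | 0.20 | 0.38 / 0.90 | 42.2% | 2.2 points |
| 0.10 | 0.10 | 0.39 / 0.90 | 43.3% | 3.3 points |
| 0.20 | 0.20 | 0.36 / 0.80 | 45.0% | 5.0 points |
| 0.20 | 0.10 | 0.38 / 0.80 | 47.5% | 7.5 points |

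**Outcomes obtained.** If the lost men are still surveyed, the arm total is (1 − d) × observed + d·u. For the first row this is 0.38 + 0.02 = 0.40, so the bias is zero.

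**Outer case.** Suppose every decliner is a non-tester and is dropped. With p = 0.40, losing 5 of 50 gives 20/45 = 44.4% (+4.4 points) and losing 10 gives 20/40 = 50.0% (+10 points). The chance of a false significant result favouring STOS (two-sided 0.05 test of two proportions) is then about 6% and 16%, against a nominal 2.5%.

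**Kept in the population, outcome unknown.** The bounds on STOS uptake are 5/50 = 10 points wide for 5 such men and 10/50 = 20 points wide for 10.

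**The case against.** A reader might infer that men who decline give no follow-up data and are therefore lost from STOS alone. The documents do not say so. The verbal consent can be read as consent to the self-test session, which controls do not have. Survey consent is given separately by everyone at the start of the online survey. Follow-up surveys and retention contact cover both arms, and the primary outcome draws on self-report as well as STOS records. On that reading a man who declines the session is a non-user of the intervention whom SAP 4.1 already keeps.

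A reader might also take it as stated that consent comes after allocation, or that controls give no consent. The timing is inferred from the order of the text. E-consent, the willingness contact and the reconfirmation at follow-up all apply to controls, who can also be lost at those points. The consent sentence in Protocol 2.3.1 that requires demonstrated understanding names no arm.

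Finally, the size rests on assumed inputs, and selective loss of controls could offset it. Even 7.5 points is below one standard error of the difference at 50 per arm and 40% uptake: √(2 × 0.40 × 0.60 / 50) = 9.8 points. The trial is a pilot with a feasibility aim.

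All of this stands as a limit on the claim, but it does not remove the gap. The text as it runs puts an eligibility check and a consent step after assignment in one arm, Protocol 2.4.2 conflicts with SAP 4.1 on who is compared, and no rule covers refusers. A bias smaller than the standard error is still systematic, and it would be hard to see in the results.

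**Conclusion.** The point holds as a flaw in sequence with a missing rule, not as a demonstrated loss from one arm. As written, a second eligibility confirmation and verbal consent follow assignment for STOS men only, and the order of contact, consent and randomisation is left open elsewhere. Men who stop at that step are not automatically excluded, but they may be replaced or give no outcome data.

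If they are lost, the bias favours STOS. The 2 to 7.5 points is an illustration that depends on 40% uptake, 10–20% loss, 10–20% uptake among those lost, and no selective loss of controls. It falls to zero if those men stay in and their outcomes are obtained. The protection is inexpensive and standard, so the change should be made.

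**What to change.** 1. Use the staff contact already in Protocol 2.3.1 to confirm eligibility and take trial consent from every man before allocation is made or revealed, and randomise only then. State this order in Protocol 2.1.1 and 2.3.1. Leave only the scheduling of the STOS session after allocation.
2. Align Protocol 2.4.2 with SAP 4.1, so that the STOS group is everyone allocated to it who completed baseline, whether or not a kit was sent.
3. State that a man who refuses the STOS session stays in his arm, is not replaced, and is offered the same 6- and 12-month surveys as everyone else.
4. Report refusals and failed checks after allocation by arm. These counts also serve the feasibility and acceptability aim (Protocol 1.4, Aim 3).

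The cost is a short call for controls. Some men will drop out before randomisation and must be replaced to reach 100, but that loss comes before allocation and cannot unbalance the arms. If staff already work in this order, a clarifying sentence on sequence is enough for item 1, and items 2 to 4 remain text changes.
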